### **Procedures**

1. Patients who meet the criteria and agree to participate in the study taken as the subject of the research.
2. Research subjects were then randomized into two groups. The control group (Group A) and the treatment group (Group B) as the group that receiving intra aortic balloon pump (IABP) as early as possible within 3 hours after the return of spontaneous circulation (ROSC). IABP insertion is performed by an interventionist.
3. Baseline data such as age, weight, height, risk factor (hypertension, Diabetes Mellitus,

dyslipidemia, smoking, family history), history of Acute Myocardial Infarct (AMI), Percutaneous Coronary Intervention (PCI), Coronary Artery Bypass Graft (CABG), and valvular disease will be taken. Vital signs examination and EKG 12 leads will be performed.

- Laboratory tests for peripheral venous blood include: Lactate levels, urea (Ur), creatinine (Cr), n-terminal pro B-type natriuretic peptide (NT Pro BNP), high sensitive troponin (Hs Trop), IL-6, beclin 1 and caspase 3.
  - Central venous blood examination for central venous blood gas analysis includes assessment of a-vO2 diff and ScvO2.
  - Arterial blood examination for arterial blood gas analysis.  
Monitoring of hemodynamic parameters using echocardiography machines (ejection fraction, TAPSE, cardiac output, VTI).
4. In the group B, IABP is initiated within 3 hours after the return of spontaneous circulation by the interventionist.
  5. Blood sampling is repeated at 6th hour post ROSC or 1 hour post-insertion of IABP consisting of:
    - Laboratory tests for peripheral venous blood include lactate, IL-6, beclin-1 and caspase 3 levels.
    - Central venous blood examination for central venous blood gas analysis includes assessment of a-vO2 diff and ScvO2.
    - Arterial blood examination for arterial blood gas analysis.  
Examination of hemodynamic parameters with echocardiographic machine was repeated at the 6th hour post ROSC, consisting of ejection fraction, TAPSE, cardiac output, VTI).
  6. Research subjects will be monitored during hospitalization.

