### **Analysis Method**

Data analysis using SPSS 20.0 software program with appropriate statistical test. Data taken during the study will be displayed according to the variable type. Numerical variables with normal distribution will be displayed as mean  $\pm$  standard deviation, which is then analyzed by a general linear model (GLM) test for data measured more than once (IL-6, Beclin-1, Caspase-3, a- vO2 diff, and ScvO2) and independent t test for data with one time measurement (mortality rate in hospital and effective lactate clearance). Numerical variables with abnormal distribution will be shown in median (minimum-maximum) and then analyzed by Mann-Whitney test. The categorical variable will be displayed as a percentage (number) and will be analyzed by chi-square test or alternate test.

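### Baseline bloods and echocardiography are listed after randomisation with no set time from ROSC, so baseline timing can differ by arm and bias the repeated blood measures

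*Combined protocol and SAP*

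**What the plan says.** The Procedures section is a numbered list. Item 1 covers eligibility and agreement. Item 2 states "Research subjects were then randomized into two groups" and defines Group B as receiving the balloon pump "as early as possible within 3 hours after the return of spontaneous circulation (ROSC"). Item 3 opens with "Baseline data such as age, weight, height, risk factor" and continues with history, vital signs, a 12-lead ECG, peripheral venous bloods including lactate, central venous and arterial gases, and echocardiography. It gives no clock time or window for any of these. Item 4 then reads: "In the group B, IABP is initiated within 3 hours after the return of spontaneous circulation by the interventionist". Item 5 repeats the bloods either 6 hours after ROSC or 1 hour after insertion, and the echocardiogram at 6 hours.

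The Analysis Method section assigns IL-6, beclin-1, caspase-3, a-vO2 diff and ScvO2 to a general linear model for data measured more than once. It assigns "effective lactate clearance" to a t test and does not define it. The Primary Outcome section names in-hospital mortality. Blinding is not mentioned anywhere.

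**The concern.** A baseline taken before allocation cannot depend on the arm, so any difference in its timing between arms is due to chance. A baseline taken after allocation loses that protection. Here the two arms also work under different time pressure. In Group B the baseline has to be fitted in ahead of an insertion with a deadline, while nothing sets a clock for Group A.

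Each named blood measure has only two scheduled values, and baseline is the first. If lactate or a marker is changing in the hours after ROSC, a systematic difference between arms in when that first value is drawn becomes a difference in change that the analysis cannot tell from an effect of the pump. These measures are the planned evidence for the stated aim of better circulation and tissue perfusion.

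**Working it through.** **Order and timing, from Procedures**

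| Step | Item | Time set |
|---|---|---|
| Randomisation | 2 | none |
| Baseline bloods, gases, ECG, echocardiography | 3 | none |
| Insertion, Group B only | 4 | within 3 h of ROSC |
| Second bloods | 5 | 6 h after ROSC, or 1 h after insertion |
| Second echocardiogram | 5 | 6 h after ROSC |

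As numbered, baseline follows allocation and precedes insertion. No step requires baseline to be complete before allocation.

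**Size.** The plan gives no figure to reproduce: no sample size, variability or expected clearance is stated. What follows is an illustration on assumed values.

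Assumptions not taken from the documents:
- lactate falls exponentially at rate k per hour, the same in both arms (no treatment effect);
- clearance is the proportional fall from baseline to the second sample;
- baseline is at 0.5 h after ROSC in Group B and 1.5 h in Group A. This direction is arbitrary.

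Formula: clearance = 1 − exp(−k × (t2 − t0)), where t0 is the baseline time and t2 the second-sample time.

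*Case 1: second sample at 6 h in both arms.* The intervals are 6 − 0.5 = 5.5 h (B) and 6 − 1.5 = 4.5 h (A).

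| k | B | A | B − A |
|---|---|---|---|
| 0.05 | 24.0% | 20.1% | +3.9 points |
| 0.10 | 42.3% | 36.2% | +6.1 points |
| 0.20 | 66.7% | 59.3% | +7.4 points |

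For k = 0.10: 1 − exp(−0.55) = 42.3% and 1 − exp(−0.45) = 36.2%. With baselines half an hour apart (0.5 h and 1.0 h), the gaps are 1.9, 3.0 and 3.5 points.

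*Case 2: Group B sampled 1 h after insertion.* With insertion at the 3-hour limit, the second sample falls at 3 + 1 = 4 h, so B's interval is 4 − 0.5 = 3.5 h. Group A stays at 6 h.

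| k | B | A | B − A |
|---|---|---|---|
| 0.05 | 16.1% | 20.1% | −4.1 points |
| 0.10 | 29.5% | 36.2% | −6.7 points |
| 0.20 | 50.3% | 59.3% | −9.0 points |

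(Differences are taken before rounding.) The baseline times are the same as in Case 1, but the sign is reversed.

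*Case 3: clearance expressed per hour of interval, k = 0.10, times as in Case 1.* B: 42.3 / 5.5 = 7.7% per hour. A: 36.2 / 4.5 = 8.1% per hour. The gap is small and runs against B.

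**The case against.** The strongest reply is that the order rests on list numbering alone. Item 2 largely defines the groups, item 3 is one step common to both arms, and nothing says baseline is handled differently by arm. That is fair as far as it goes: the text shows that timing could differ, not that it does. It does not remove the gap, because items 4 and 5 are timed and baseline is not.

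A reader might infer more than the documents support:

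- *Group A's baseline is drawn later, so the bias favours Group B.* The different time pressure makes this conceivable, but the documents do not state it. Cases 2 and 3 show that the net direction also depends on the second-sample time and on how clearance is defined.
- *Readings are taken with allocation known.* The documents are silent. Bedside blinding is implausible with no sham described, but who reads the echocardiograms or runs the assays, and what they know, is not stated.
- *Every change measure is affected, including echocardiography.* Analysis Method names no analysis of echocardiographic change. The measures it does name are assays and blood gases, which are exposed mainly through sampling time.
- *Baseline is contaminated by the device.* The list puts baseline before insertion.

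A practical objection also stands. If allocation comes first, preparation for insertion can overlap with baseline collection. Requiring a completed baseline before allocation could remove that overlap, so the fix needs an alternative.

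**Conclusion.** The point holds for timing. Baseline is listed after allocation with no time from ROSC, and only one arm is under a time limit, so an arm-dependent baseline time is possible and nothing in the plan prevents it. It would affect the five repeated blood measures and, if clearance is calculated from the baseline value, effective lactate clearance. It does not affect in-hospital mortality, which uses no baseline reading.

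The size is illustrative. A one-hour difference moves apparent clearance by about 4 to 7 points, given assumed exponential decay of 0.05 to 0.20 per hour, a proportional definition of clearance and a common 6-hour second sample. Neither the size nor the sign can be taken as a prediction for this trial, because the second-sample rule can reverse it. The change is worth making for the biomarker results, but it does not threaten the primary comparison.

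**What to change.** Reorder Procedures so that, after consent, the baseline bloods, gases, ECG and echocardiogram are completed and only then is the allocation opened. If this would delay preparation for insertion, keep the current order and set one baseline window, counted from ROSC, that applies to both arms. The window is the weaker remedy, since timing can still differ by arm inside it. In the illustration, baselines half an hour apart still shift clearance by 1.9 to 3.5 points, so the window should be narrow.

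Under either option, record the clock times of ROSC, baseline sample, allocation and second sample for every patient, so that the intervals can be compared by arm. The two alternatives for the second blood sample in item 5 must also be reconciled, because fixing baseline alone leaves the other end of the interval open. The protocol should define lactate clearance and say whether echocardiogram readers know the allocation.

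The cost is one reordered step and a few time fields. Baseline is already listed before insertion, so little or no delay is expected unless preparation depends on knowing the allocation early. A small downside of the reorder is that a few patients will have baseline samples drawn and then not be randomised.

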### **Inclusion and Exclusion Criteria**

#### **Inclusion Criteria**

1. Cardiac arrest survivor patients with acute coronary syndrome
2. Age over 18 years and less than 75 years

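### The baseline list names no characteristic of the cardiac arrest itself and mortality is tested unadjusted, which costs precision and leaves a chance imbalance in arrest severity unexamined

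*Combined protocol and SAP*

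**What the plan says.** The Inclusion Criteria define the population as "Cardiac arrest survivor patients with acute coronary syndrome", aged between 18 and 75. Neither they nor the Exclusion Criteria restrict place of arrest or time to ROSC. Rhythm is touched only indirectly, through the exclusion of Brugada and congenital long QT syndromes.

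Procedures item 3 begins "Baseline data such as age, weight, height, risk factor", gives five coronary risk factors, and continues: "history of Acute Myocardial Infarct (AMI), Percutaneous Coronary Intervention (PCI), Coronary Artery Bypass Graft (CABG), and valvular disease will be taken". It adds "Vital signs examination and EKG 12 leads will be performed", then peripheral bloods (including lactate, creatinine, NT-proBNP and troponin), central venous and arterial blood gases, and echocardiography. ROSC appears in Procedures only as the start of the clock for pump insertion and repeat measurement.

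On allocation, item 2 says "Research subjects were then randomized into two groups", with no stratification factor. The Analysis Method assigns mortality to an "independent t test for data with one time measurement (mortality rate in hospital and effective lactate clearance") and gives chi-square or an alternative for categorical variables. It mentions no covariate-adjusted model for mortality. The Primary Outcome is in-hospital mortality.

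**The concern.** Every patient qualifies through a cardiac arrest, and the chance of dying in hospital plausibly depends on how long and how severe that arrest was. The documents give no figure for this; it is a clinical expectation. Eligibility lets these features vary widely, yet the protocol does not ask for any of them.

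Two things are at stake. First, the report could not show whether the arms were alike in arrest severity, which is among the first things a reader of this trial will ask. Second, a model for death that used these features would estimate the pump effect more precisely than the planned comparison of two raw percentages. The markers that are listed capture arrest severity only in part. The 12-lead ECG taken at enrolment, for example, is not the first rhythm recorded during the arrest.

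**Working it through.** **Is anything about the arrest specified?** All sections were read for arrest characteristics, stratification and adjustment.

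| Item | Named in the protocol? |
|---|---|
| Time of collapse, collapse-to-ROSC interval | No |
| Clock time of ROSC | Not as a data item, but needed to apply the 3-hour and 6-hour windows |
| First recorded rhythm | No |
| Witnessed arrest, bystander resuscitation | No |
| In- or out-of-hospital arrest | No |
| Stratified randomisation | No |
| Covariate-adjusted mortality analysis | No |

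**Is there a figure to reproduce?** No. The documents state no sample size, event rate, effect size or power. Everything below rests on assumptions and shows scale only.

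**How often would a chance imbalance arise?** Assume a yes/no arrest feature present in half of patients and equal arms of n. With X and Y independent Binomial(n, 0.5), the exact probability that |X − Y|/n reaches a given gap is:

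| n per arm | Gap ≥ 10 points | Gap ≥ 20 points |
|---|---|---|
| 30 | 0.52 | 0.16 |
| 50 | 0.37 | 0.06 |
| 100 | 0.18 | 0.006 |

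At 30% prevalence the 10-point figures are 0.48, 0.33 and 0.14.

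**What would such a gap do?** Shift in the mortality difference = imbalance × mortality gap between levels of the feature. With an assumed gap of 20 to 40 points, a 10-point imbalance gives 0.10 × 20 = 2 to 0.10 × 40 = 4 points.

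Compare the standard error of the mortality difference at 50% mortality, √(2 × 0.25/n): 12.9 points at n = 30, 10.0 at n = 50 and 7.1 at n = 100. That standard error already contains shifts of this kind.

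**What precision is given up?** Simulated trials (1,500 per setting) used a logistic outcome with these assumptions:
- control mortality about 50%, conditional treatment odds ratio 0.4;
- log-odds per SD of time to ROSC 0.5 (moderate) or 0.8 (strong), that is odds ratios e^0.5 = 1.65 or e^0.8 = 2.2;
- log-odds for rhythm 0.7 or 1.1 (odds ratios about 2 or 3), prevalence 50%;
- log-odds 0.3 per SD of age and 0.4 per SD of lactate; correlation of lactate with time 0.4.

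Wald-test power for treatment (%):

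| n per arm, strength | Unadjusted | Age + lactate | Age + lactate + time + rhythm | Gain over age + lactate |
|---|---|---|---|---|
| 50, moderate | 49.2 | 51.2 | 52.9 | 1.7 |
| 50, strong | 43.5 | 45.9 | 50.1 | 4.2 |
| 100, moderate | 77.2 | 79.5 | 81.1 | 1.6 |
| 100, strong | 71.6 | 75.1 | 80.3 | 5.2 |

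Each entry has a simulation standard error of up to √(0.25/1,500) = 1.3 points. A second run with 3,000 trials per setting gave, for the last step, 51.0 to 52.9, 42.7 to 47.6, 79.9 to 82.0 and 73.9 to 79.0, so the gains agree within that error. Across repeated runs the gain over age and lactate is about 1 to 6 points. A model with treatment and the two arrest variables alone gains roughly 3 to 7 points over the unadjusted test at 30 to 100 per arm, with type I error near 5%.

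**The case against.** The other side has several good points.

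- **The list is open.** Its items are introduced as examples. A reader might infer that arrest data will never be captured, but the documents do not show the case form and cannot support that. What stands is narrower: the protocol specifies none of these items, although it is detailed enough to name individual echocardiographic measures and biomarkers.
- **Severity is partly measured.** Lactate, blood gases, vital signs, troponin, ejection fraction and cardiac output reflect perfusion and heart function after the arrest. This is true and it reduces the loss. Even so, the simulation shows a further gain after lactate and age, under its assumptions.
- **Randomisation protects the test.** A reader might infer that an unseen imbalance biases the result. It does not: chance imbalance is already within the error rate of the unadjusted comparison, and a 2 to 4 point shift is small beside a standard error of 7 to 13 points.
- **The loss may be repairable.** Where a resuscitation record exists, rhythm, place and witness status could probably be abstracted later. A reader might infer that no later analysis could recover the position; that goes too far. Prospective capture is still preferable, because abstraction then precedes knowledge of the outcome.
- **The gain is modest and assumed.** That is correct. It also appears only if the analysis plan uses the variables; listing them is not enough.

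**Conclusion.** The point holds as a matter of efficiency and transparency. No arrest characteristic is specified, randomisation is not stated to be stratified, and mortality is to be tested without adjustment. The planned comparison remains valid. What it gives up is precision, plus the ability to examine an imbalance in arrest severity under the protocol as written.

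The size is roughly 3 to 7 points of power against the planned unadjusted test at 30 to 100 per arm, and about 1 to 6 points against a model already using age and lactate. These figures depend on assumed arm sizes, about 50% control mortality, a large treatment effect and the stated prognostic odds ratios, none of which comes from the documents. Weaker prognostic effects would shrink the gain. The change is still worth making because it costs so little.

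**What to change.** **Procedures, item 3.** Add to the baseline data, taken from the resuscitation record before the outcome is known: clock times of collapse and of ROSC (hence the interval), first recorded rhythm (shockable or not), witnessed or bystander status, and in- or out-of-hospital arrest. Give each an unknown category.

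**Analysis Method.** Tabulate these items by arm. Pre-specify one logistic model for in-hospital mortality, with treatment, collapse-to-ROSC time and first rhythm, as the primary comparison. Report the adjusted risk difference and odds ratio from it. Keep the unadjusted percentages and chi-square test as supporting results, and say that the model decides, so that two analyses do not compete. State how an unknown collapse time enters the model, for example as an indicator alongside a fixed value.

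**Cost.** A few form fields and a few lines of analysis text; no extra procedures or patients. The ROSC time is already needed for the protocol's time windows, but collapse time and the other items are not implied by it and must be sought. In unwitnessed arrests the collapse time will be estimated or unknown, which trims the gain.

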### **Aim**

To observe the effects of intra aortic balloon pump on clinical outcomes of cardiac arrest patients and prognosis improvement through circulation and tissue perfusion improvement.

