### **Primary Outcome**

In-hospital mortality

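### The repeat blood draw has two alternative times and no rule by arm, so marker comparisons can confound the IABP effect with at least about 2 hours of elapsed time

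*Combined protocol and SAP*

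**What the plan says.** Three parts of the Procedures section bear on the timing.

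- Item 5, repeat blood: "Blood sampling is repeated at 6th hour post ROSC or 1 hour post-insertion of IABP consisting of" peripheral venous markers (lactate, IL-6, beclin-1, caspase 3), central venous gases (a-vO2 difference, ScvO2) and arterial gases. It does not say which time belongs to which arm, or which applies in Group B when both are possible.
- Item 4, device timing: "In the group B, IABP is initiated within 3 hours after the return of spontaneous circulation by the interventionist".
- Item 5, repeat echocardiography: "Examination of hemodynamic parameters with echocardiographic machine was repeated at the 6th hour post ROSC". Here there is one time and no alternative.

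The Analysis Method section assigns the repeated markers to a "general linear model (GLM) test for data measured more than once". Lactate clearance goes to an "independent t test for data with one time measurement (mortality rate in hospital and effective lactate clearance"). For skewed data: "Numerical variables with abnormal distribution will be shown in median (minimum-maximum) and then analyzed by Mann-Whitney test". None of these analyses is given a term or rule for the actual time of sampling. Effective lactate clearance is not defined.

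The Aim section includes "prognosis improvement through circulation and tissue perfusion improvement". The Primary Outcome section names "In-hospital mortality" alone.

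**The concern.** The second of the two permitted times is counted from IABP insertion, an event that defines Group B. A control patient without an IABP has no such clock and can only be sampled at 6 h. The most natural reading of the sentence is therefore arm-specific: 6 h for Group A and 1 h after insertion for Group B. On that reading elapsed time since ROSC is completely tied to treatment arm. In the GLM, the second measurement would mean 6 h in one arm and 4 h or earlier in the other.

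Randomisation gives no protection, because the difference is created after randomisation by the sampling schedule. Later adjustment gives little: when time and arm coincide, separating them depends on modelling assumptions, and the Mann-Whitney test takes no covariate.

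At stake are the between-arm comparisons of lactate clearance, IL-6, beclin-1, caspase-3, a-vO2 difference and ScvO2. Apart from the echocardiogram, these are the repeat measurements that could support the circulation and perfusion part of the aim. A marker that is simply falling or rising after resuscitation could make the device look harmful or helpful with no true effect.

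**Working it through.** **Inputs from the documents**

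- Repeat draw: 6 h after ROSC, or 1 h after IABP insertion (Procedures, item 5).
- IABP start in Group B: *t* hours after ROSC, with *t* at most 3 (Procedures, item 4).

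The plan states no figure of its own to reproduce: no sample size, marker variability or expected marker effect is given.

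**Step 1. Size of the time gap.** Under the 1-hour option the Group B sample falls at *t* + 1. The gap to a 6 h control sample is 6 − (*t* + 1) = 5 − *t* hours.

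| IABP at (h) | Group B sample (h) | Group A sample (h) | Gap (h) |
|---|---|---|---|
| 3 | 4 | 6 | 2 |
| 2 | 3 | 6 | 3 |
| 1 | 2 | 6 | 4 |

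The two options coincide only when 5 − *t* = 0, that is for insertion at 5 h, which is outside the 3 h window.

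**Step 2. What the possible readings imply.**

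- Group A at 6 h, Group B at 1 h after insertion: time is fully confounded with arm.
- Free choice within Group B: sampling times in that arm range from about 1 h to 6 h, and the choice could depend on the patient's condition.
- Both arms at 6 h: no gap, but nothing in the text requires this.

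**Step 3. Illustration for a marker level.** *Assumptions:* no IABP effect, the same constant percentage change *r* per hour in both arms, and a 2 h gap. The ratio of Group B to Group A is (1 − *r*)^−2 for a falling marker and (1 + *r*)^−2 for a rising one. The baseline time cancels.

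| *r* per hour | Falling: B/A | Rising: B/A |
|---|---|---|
| 5% | 1.108 (11% higher) | 0.907 (9% lower) |
| 10% | 1.235 (23% higher) | 0.826 (17% lower) |
| 15% | 1.384 (38% higher) | 0.756 (24% lower) |

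**Step 4. Illustration for lactate clearance.** *Further assumption:* baseline draw at 0.5 h after ROSC. Total clearance at time *s* is 1 − (1 − *r*)^(*s* − 0.5). With *r* = 10%:

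- Group A, *s* = 6: 1 − 0.9^5.5 = 44.0%.
- Group B, IABP at 3 h, *s* = 4: 1 − 0.9^3.5 = 30.8%, a spurious deficit of 13.1 points.
- Group B, IABP at 1 h, *s* = 2: 1 − 0.9^1.5 = 14.6%, a spurious deficit of 29.4 points.

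With IABP at 3 h and other rates, the deficit is 24.6% − 16.4% = 8.2 points at 5% per hour and 59.1% − 43.4% = 15.7 points at 15%.

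If clearance is instead expressed per hour, the sign reverses. At *r* = 10%, Group A shows 43.98/5.5 = 8.00% per hour, against 30.84/3.5 = 8.81 (IABP at 3 h) and 14.62/1.5 = 9.75 (IABP at 1 h) in Group B. That is a spurious relative gain of 10% to 22%. Since the plan does not define the measure, even the direction of the bias is open.

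**The case against.** The strongest reply is that the problem is conditional and peripheral. The wording permits sampling everyone at 6 h, and then there is no bias. The primary outcome does not depend on blood sampling, the echocardiographic measures of circulation are fixed at 6 h, and no marker is named as a secondary outcome. This stands as a limit on importance. It does not remove the defect, because following the schedule as written can produce the imbalance.

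The 2 h minimum is also not strict. The control group's care is not described, so a later IABP there is neither planned nor excluded, and starting a device may differ from completing its insertion. If insertion were complete at 3.5 h, for example, the gap would be 1.5 h. Hence *about* 2 h.

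The illustrative rates are not from the documents, and constant percentage change does not suit every marker. A saturation such as ScvO2 rising 10% per hour from an assumed 60% would exceed 100% after 5.5 h (60% × 1.1^5.5 is about 101%). The 29-point figure needs a very early insertion. These points stand: only the time gap follows from the documents.

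A sample 1 h after insertion may be deliberate, to catch an early device effect. That is a reason to keep it within Group B. It does not make that sample comparable with a 6 h control sample.

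Finally, fixing the second draw leaves the baseline time open. This is correct: change-based measures will still cover unequal intervals if baseline timing differs by arm.

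**Conclusion.** The concern holds. The schedule allows the repeat sample to be taken at least about 2 h earlier in Group B than in Group A, and the analysis section does nothing about it. The figure assumes that the 1-hour option is used, that IABP insertion falls inside the 3 h window, and that controls are sampled at 6 h. If Group B is sampled at 6 h the gap is zero.

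The resulting bias in any marker cannot be estimated from the documents. Under the assumed rates it is large enough to matter, and its direction depends on the marker's course and, for lactate, on an unstated definition. In-hospital mortality, the 6 h echocardiogram and the tests done only at baseline are untouched. The change should be made to protect the marker comparisons; the primary analysis does not depend on it.

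**What to change.** 1. In Procedures, item 5, name the plan's own 6 h after ROSC as the repeat draw in both arms for all between-arm comparisons, and remove the alternative tied to insertion. If a sample 1 h after insertion is wanted, list it separately as descriptive within Group B. This removes the scheduled gap in the second draw whichever test is used.
2. Record the actual clock times of the baseline and repeat draws relative to ROSC.
3. Define effective lactate clearance once, as the percentage fall from the baseline draw to the 6 h sample. If a threshold category was intended, state the cut-off and base it on the same two draws.
4. Optionally, adjust for draw interval or baseline draw time as a sensitivity analysis. It should not be the main analysis: the baseline draw is listed after randomisation, and the Mann-Whitney branch cannot accommodate it.

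The cost is a wording change, one definition and two recorded times, with no extra draw unless the 1-hour Group B sample is also kept. There are two downsides. There would be no 1-hour reading in the between-arm comparison. Group B patients who die between the 1-hour point and 6 h would have no repeat sample, as already holds for Group A deaths before 6 h. The number without a 6 h sample should be reported by arm.
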